The analyses will be conducted independently for the different patient groups. To support construct validity and responsiveness of EQ-5D-3L and EQ VAS in each patient group, 75% of the hypotheses will need to be supported [6–9]. Historical registry data from the Swedish Rheumatology Register (SRQ) will be used to assess the construct validity and responsiveness of EQ-5D-3L and EQ VAS. Data on EQ-5D-3L has been collected since 2008 [10] and the study will include data from 2008 until the time of data extraction.

Ethical approval has been granted for the project (2023-04394-01).

Karolinska Institutet – Research protocol: Follow-up with patient-reported outcome measures for improved health related quality of life – Construct validity and responsiveness of EQ-5D-3L in patients with rheumatic disease

Study population

Inclusion criteria are:

- 18 years and older at the time of first included measurement
- A diagnosis of RA, polyarthritis, PsA, or AS
- Complete registration of responses in the EQ-5D-3L descriptive system or EQ VAS on at least one time point in SRQ
- For patients with RA: At least one measurement with Disease Activity Score 28 (DAS28) reported in relation to the same visit as EQ-5D-3L
- For patients with polyarthritis: At least one measurement with DAS28 reported in relation to the same visit as EQ-5D-3L
- For patients with PsA: At least one measurement with DAS28 or Disease Activity in Psoriatic Arthritis (DAPSA) reported in relation to the same visit as EQ-5D-3L
- For patients with AS: At least one measurement with the Bath Ankylosing Spondylitis Disease Activity Index (BASDAI) reported in relation to the same visit as EQ-5D-3L

For the analyses of construct validity, the latest measurement will be used if the individual patients have multiple complete registrations with EQ-5D-3L and the other required measure. The hypotheses for responsiveness will be tested in patients with newly diagnosed disease (having the diagnosis for ≤ 12 months), as changes in disease activity are likely to be present in this group. For the analysis of responsiveness, the two first measurements during the first year will be used.

Outcome measures

EQ-5D-3L and EQ VAS

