The EQ-5D-3L measures HRQoL and consists of two parts. The first part contains five questions about mobility, daily activities, self-care, pain/discomfort, and anxiety/depression [11, 12]. Each question can be answered with no problem (1), some/moderate problem (2) unable to perform certain activities/having extreme problems (3). The answers can be summarized in an index value based on an existing preference-based value set. In this study, the EQ-5D-3L value set by Dolan [13] will be used for the main analyses and a Swedish experience-based value set in a sensitivity analysis [14]. For the EQ-5D-3L index, 1 represents full health and 0 represents a value equal to being dead. EQ VAS measures the persons

Karolinska Institutet – Research protocol: Follow-up with patient-reported outcome measures for improved health related quality of life – Construct validity and responsiveness of EQ-5D-3L in patients with rheumatic disease

health today on a visual analogue scale (VAS) from 0 (worst imaginable health) to 100 (best imaginable health) [11, 12].

Disease activity

DAS28 was developed for patients with RA and contains questions about tender and swollen joints, disease activity and inflammation [15]. DAPSA was developed for patients with PsA and contains questions about tender and swollen joints, disease activity, pain, and inflammation [16, 17]. BASDAI was developed to measure disease activity in patients with AS and contains questions about fatigue, pain, swelling and stiffness [18, 19]. ASDAS was developed to measure disease activity in patients with AS and contains questions about pain, swelling, stiffness, disease activity and inflammation [20].

For all these measures, a higher value indicates higher disease activity.

Functional ability

The Health Assessment Questionnaire Disability Index (HAQ-DI) and the Bath Ankylosing Spondylitis Functional Index (BASFI) measure functional ability through questions about mobility, daily activities, and self-care [19, 21]. For both scales, a higher value indicates more problems with functional ability.

VAS questions

The SRQ also contains three questions about pain, fatigue, and general health (global score), measured on a VAS. The questions ask how much pain the person has had, how fatigue they have been and how their general health has been in the last week due to their rheumatic disease. The scale ranges from no problem (0) to as bad as it can be (100) [22].

Hypotheses

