To assess the magnitude of the differences in the proportions of reported problems in the EQ-5D-3L dimensions between groups, the effect size (r) will be calculated. The effect size is considered small if it is ≥ 0.1 , medium if it is ≥ 0.3 and large if it is ≥ 0.5 [30–32]. To support the hypotheses for the dimensions, at least a small effect size will be required.

To estimate whether there is a difference in the EQ-5D-3L mean index value between groups, cut-off values for minimally important differences (MID) will be used. Minimal important differences represent the smallest improvement considered worthwhile by a patient [33]. The MID values used in this study will be based on the literature.

The hypotheses for known-groups validity of EQ-5D-3L are presented in the text below.

Karolinska Institutet – Research protocol: Follow-up with patient-reported outcome measures for improved health related quality of life – Construct validity and responsiveness of EQ-5D-3L in patients with rheumatic disease

DAS28/DAPSA

- Lower EQ-5D-3L **index** values are expected in patients with moderate/high disease activity compared to patients in remission/with low disease activity.
- More reported problems in EQ-5D-3L **mobility** are expected for patients with moderate/high disease activity compared to patients in remission/with low disease activity.
- More reported problems in EQ-5D-3L **self-care** are expected for patients with moderate/high disease activity compared to patients in remission/with low disease activity.
- More reported problems in EQ-5D-3L **daily activities** are expected for patients with moderate/high disease activity compared to patients in remission/with low disease activity.
- More reported problems in EQ-5D-3L **pain/discomfort** are expected for patients with moderate/high disease activity compared to patients in remission/with low disease activity.

ASDAS

- Lower EQ-5D-3L **index** values are expected in patients with high/very high disease activity compared to patients with inactive disease/low disease activity.
- More reported problems in EQ-5D-3L **mobility** are expected in patients with high/very high disease activity compared to patients with inactive disease/low disease activity.
- More reported problems in EQ-5D-3L **self-care** are expected in patients with high/very high disease activity compared to patients with inactive disease/low disease activity.

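### The AS inclusion criterion accepts only BASDAI, so AS patients with ASDAS but never BASDAI at an EQ-5D-3L visit are lost even to the ASDAS hypotheses

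*Combined protocol and SAP*

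**What the plan says.** The Study population section opens its list with "Inclusion criteria are" and does not limit the list to particular analyses, so the criteria govern the whole study.

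- For AS the disease-activity line reads "For patients with AS: At least one measurement with the Bath Ankylosing Spondylitis Disease Activity Index (BASDAI) reported in relation to the same visit as" (the visit being that of EQ-5D-3L). ASDAS is not offered as an alternative.
- For PsA it reads "At least one measurement with DAS28 or Disease Activity in Psoriatic Arthritis (DAPSA) reported in relation to the same visit as EQ-5D-3L". Either score is enough.
- For rheumatoid arthritis (RA) and polyarthritis the only score named is DAS28.

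The Disease activity section presents ASDAS as a measure for AS in its own right: "ASDAS was developed to measure disease activity in patients with AS and contains questions about pain, swelling, stiffness, disease activity and inflammation". The section Known-groups validity EQ-5D-3L splits ASDAS at 2.1 and gives it a separate block of hypotheses, beginning "Lower EQ-5D-3L index values are expected in patients with high/very high disease activity compared to patients with inactive disease/low disease activity". ASDAS is also named in the convergent-validity, change-correlation and AUC hypotheses, for both EQ-5D-3L and EQ VAS.

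The visit used for construct validity is set by this rule: "the latest measurement will be used if the individual patients have multiple complete registrations with EQ-5D-3L and the other required measure".

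**The concern.** Eligibility and hypotheses do not match. The plan sets out to test EQ-5D-3L and EQ VAS against ASDAS, but a patient with exactly the data that test needs (EQ-5D-3L and ASDAS at one visit) cannot enter the study without a BASDAI at some EQ-5D-3L visit. The plan does not relax this for the ASDAS hypotheses and does not explain it. For PsA, the other group with two scores, it chose the opposite rule.

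What is at stake is usable registry data. The ASDAS hypotheses count towards the 75% support rule, which is applied in each patient group. They would be judged only in the AS patients who also had BASDAI recorded at some point.

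**Working it through.** The plan states no figure on this point that could be reproduced. The check compares eligibility with use, counts the hypotheses, and asks who is lost.

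**1. Eligibility against use**

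| Group | Disease-activity scores used | Score that admits a patient |
|---|---|---|
| RA, polyarthritis | DAS28 | DAS28 |
| PsA | DAS28, DAPSA | either |
| AS | BASDAI, ASDAS | BASDAI only |

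AS is the only group in which a score has hypotheses but does not admit a patient.

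**2. Hypotheses that use ASDAS**

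| Domain | EQ-5D-3L | EQ VAS |
|---|---|---|
| Convergent validity (slash-separated list) | 5 | 1 |
| Known-groups validity (dedicated ASDAS block) | 5 | 1 |
| Correlation of changes (slash-separated list) | 5 | 1 |
| AUC (slash-separated list) | 1 | 1 |
| Total | 16 | 4 |

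The dedicated blocks give 5 + 1 = 6. Counting each listed score as its own hypothesis gives 16 + 4 = 20. The plan does not say how the lists are to be counted, so the defensible statement is six for certain and up to 20.

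**3. Who is lost**

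Classify AS patients by whether each score was ever recorded at an EQ-5D-3L visit, other criteria being met.

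| BASDAI ever | ASDAS ever | Now | With BASDAI or ASDAS |
|---|---|---|---|
| yes | yes | included | included |
| yes | no | included | included |
| no | yes | **excluded** | **included** |
| no | no | excluded | excluded |

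Only the third row changes. One BASDAI at any EQ-5D-3L visit keeps the patient in, even if other visits carry ASDAS alone.

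**4. How many**

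The documents give no AS patient numbers by score. Let p be the share of the third row among AS patients in the first three rows, and q the share of those patients with ASDAS.

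- Share lost from AS analyses that need neither score (such as the VAS hypotheses): p, if the measure they need is equally available in all three rows.
- Share lost from the ASDAS analyses: p/q, which is at least p because q cannot exceed 1.
- Sampling error grows by 1/√(1 − share lost).

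| Assumed share lost | Growth in sampling error |
|---|---|
| 0% | 1/√1.00 = 1.000 |
| 2% | 1/√0.98 = 1.010 |
| 10% | 1/√0.90 = 1.054 |
| 20% | 1/√0.80 = 1.118 |

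These shares are assumptions, not estimates. The plan sets no precision target, and its hypotheses are judged against thresholds (for example correlation ≥ 0.3 or ≥ 0.5, AUC ≥ 0.70). A loss of precision therefore cannot be translated into a changed verdict under the 75% rule.

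**5. Does having one score imply having the other?**

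The Disease activity section describes BASDAI as covering fatigue, pain, swelling and stiffness. It describes ASDAS as covering pain, swelling, stiffness, disease activity and inflammation. The content overlaps, so the third row may be thinly populated. But fatigue appears only under BASDAI, so on the plan's own description a recorded ASDAS does not guarantee a BASDAI.

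**The case against.** The strongest reply is that the plan does not contradict itself. An ASDAS hypothesis can be tested among patients who also have BASDAI, and a common entry score arguably keeps the AS population consistent. The two scores overlap in content, so the loss may be close to nil. The PsA comparison is also imperfect: one of the PsA scores, DAS28, was developed for RA, whereas both AS scores were developed for AS.

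Most of this stands as a limit on size. It does not supply a reason for the rule. The plan states no aim of a common sample, and the rule does not secure one: AS patients need BASDAI but not ASDAS, so the two sets of analyses can already differ. If hardly anyone is lost, the restriction also gains little.

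Two stronger readings are tempting, and the documents do not support them.

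- A reader might infer that ASDAS results are confined to visits that also recorded BASDAI. The criterion works at patient level. In the visit rule, the other required measure can reasonably be read as the one each hypothesis needs, so an ASDAS analysis may use a visit without BASDAI. The wording is open to another reading, but it does not establish the tie.
- A reader might infer that the VAS and functional-ability hypotheses in AS are wrongly gated by a score they do not use. All four patient groups must have a disease-activity score to enter, so that is the plan's general design and not a defect of the AS criterion. Accepting ASDAS as well would not remove it.

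**Conclusion.** The point holds as an unexplained mismatch between eligibility and hypotheses in one patient group. AS patients with ASDAS but never BASDAI at an EQ-5D-3L visit are excluded from all analyses, including the six dedicated ASDAS known-groups hypotheses and up to 20 ASDAS hypotheses in all. The higher figure assumes that each score in a slash-separated list is a separate hypothesis.

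The number of patients affected is unknown and may be near zero. A reader might infer a biased ASDAS result, but nothing in the documents shows how the excluded patients differ from the others, so neither a direction nor a size of bias can be derived. This is an inexpensive improvement to make before extraction, not an error that invalidates the AS analyses.

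**What to change.** In the AS line of the inclusion criteria, insert *or ASDAS* after BASDAI, keeping the link to the EQ-5D-3L visit. Then add one sentence: each hypothesis is tested in the patients with EQ-5D-3L (or EQ VAS) and that hypothesis's own measure, at the latest such visit for construct validity. The responsiveness analyses keep their rule of the first two measurements, among patients with the relevant measure at both.

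If BASDAI alone is intended, state the reason and report how many AS patients were excluded with ASDAS only.

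The cost is a few words in the protocol and the same change in the extraction request. The study is retrospective, so no new data collection is needed. The change can only keep or add patients for hypotheses that do not use BASDAI, and it leaves the BASDAI hypotheses on patients with BASDAI. The drawback is slightly different patient numbers for the BASDAI and ASDAS analyses, as can already happen for DAS28 and DAPSA in PsA. Report the number of patients for each hypothesis.

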To assess the validity and responsiveness a priori hypotheses for convergent validity, known-groups validity, and responsiveness have been formulated. The hypotheses for EQ-5D-3L are presented first followed by the hypotheses for EQ VAS.

Convergent validity EQ-5D-3L

Convergent validity will be assessed by testing hypotheses regarding the expected direction and magnitude of correlation between the EQ-5D-3L

Karolinska Institutet – Research protocol: Follow-up with patient-reported outcome measures for improved health related quality of life – Construct validity and responsiveness of EQ-5D-3L in patients with rheumatic disease

and the other outcome measures. Constructs that are considered to be related are expected to have at least a moderate correlation and constructs that are considered to be similar are expected to have a strong correlation [8]. A moderate correlation is defined as ≥ 0.3 and a strong correlation is defined as ≥ 0.5 [8]. The hypotheses for all patient groups are presented in the text below.

VAS pain

- VAS pain and EQ-5D-3L **index**: a moderate negative correlation is expected.
- VAS pain and EQ-5D-3L **mobility**: a moderate positive correlation is expected.
- VAS pain and EQ-5D-3L **self-care**: a moderate positive correlation is expected.
- VAS pain and EQ-5D-3L **daily activities**: a moderate positive correlation is expected.
- VAS pain and EQ-5D-3L **pain/discomfort**: a strong positive correlation is expected.

VAS global score

- VAS global score and EQ-5D-3L **index**: a strong negative correlation is expected.

VAS fatigue

- VAS fatigue and EQ-5D-3L **index**: a moderate negative correlation is expected.
- VAS fatigue and EQ-5D-3L **mobility**: a moderate positive correlation is expected.

Karolinska Institutet – Research protocol: Follow-up with patient-reported outcome measures for improved health related quality of life – Construct validity and responsiveness of EQ-5D-3L in patients with rheumatic disease

- VAS fatigue and EQ-5D-3L **self-care**: a moderate positive correlation is expected.
- VAS fatigue and EQ-5D-3L **daily activities**: a moderate positive correlation is expected.
- VAS fatigue and EQ-5D-3L **anxiety/depression**: a moderate positive correlation is expected.

DAS28/DAPSA/BASDAI/ASDAS

- Disease activity measured with DAS28/DAPSA/BASDAI/ASDAS and EQ-5D-3L **index**: a moderate negative correlation is expected.

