- Disease activity measured with DAS28/DAPSA/BASDAI/ASDAS and EQ-5D-3L **mobility**: a moderate positive correlation is expected.
- Disease activity measured with DAS28/DAPSA/BASDAI/ASDAS and EQ-5D-3L **self-care**: a moderate positive correlation is expected.
- Disease activity measured with DAS28/DAPSA/BASDAI/ASDAS and EQ-5D-3L **daily activities**: a moderate positive correlation is expected.
- Disease activity measured with DAS28/DAPSA/BASDAI/ASDAS and EQ-5D-3L **pain/discomfort**: a moderate positive correlation is expected.

HAQ-DI/BASFI

- Functional ability measured with HAQ-DI/BASFI and EQ-5D-3L **index**: a moderate negative correlation is expected.
- Functional ability measured with HAQ-DI/BASFI and EQ-5D-3L **mobility**: a moderate positive correlation is expected.
- Functional ability measured with HAQ-DI/BASFI and EQ-5D-3L **self-care**: a moderate positive correlation is expected.

Karolinska Institutet – Research protocol: Follow-up with patient-reported outcome measures for improved health related quality of life – Construct validity and responsiveness of EQ-5D-3L in patients with rheumatic disease

- Functional ability measured with HAQ-DI/BASFI and EQ-5D-3L **daily activities**: a moderate positive correlation is expected.
- Functional ability measured with HAQ-DI/BASFI and EQ-5D-3L **pain/discomfort**: a moderate positive correlation is expected.

Known-groups validity EQ-5D-3L

In the assessment of known-groups validity, patients will be divided into groups for which there is an expected difference in HRQoL. The groups represent patients with different levels of disease activity or functional ability. Patients with lower disease activity (<3.2 measured with DAS28, <14 measured with DAPSA, <2.1 measured with ASDAS and <4 measured with BASFI) are expected to have better health and HRQoL compared to patients with higher disease activity (≥ 3.2 measured with DAS28, >14 measured with DAPSA, ≥ 2.1 measured with ASDAS and ≥ 4 measured with BASDAI). Likewise, patients with better functional ability (<1 measured with HAQ-DI and <4 measured with BASFI) are expected to have better health and HRQoL compared to patients with worse functional ability (≥ 1 measured with HAQ-DI and ≥ 4 measured with BASFI). The cut off values for disease activity (DAS28 [23], DAPSA [24], ASDAS [25, 26], BASDAI [25–27]) and functional ability (HAQ-DI [28, 29], BASFI [27]) were taken from the literature.

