Responsiveness will be assessed in two ways. One way is by assessing the relationship between individual changes in EQ-5D-3L index value and dimensions over time with changes in other outcome measures over the same time period. The second way is to assess whether EQ-5D-3L can discriminate between patients who have improved over time and those that have not, based on changes in disease activity or functional ability.

Correlation between changes in EQ-5D-3L with changes in other outcome measurement instruments

The relationship between changes in the EQ-5D-3L and changes in other outcome measures will be assessed by analysing the correlation between the changes in the variables between the two first measurements of each individual during the first year after diagnosis. The hypotheses for expected correlations are presented in the text below.

VAS pain

- VAS pain and EQ-5D-3L **index**: the changes in scores are expected to have a moderate negative correlation.
- VAS pain and EQ-5D-3L **mobility**: the changes in scores are expected to have a moderate positive correlation.
- VAS pain and EQ-5D-3L **self-care**: the changes in scores are expected to have a moderate positive correlation.

Karolinska Institutet – Research protocol: Follow-up with patient-reported outcome measures for improved health related quality of life – Construct validity and responsiveness of EQ-5D-3L in patients with rheumatic disease

- VAS pain and EQ-5D-3L **daily activities**: the changes in scores are expected to have a moderate positive correlation.
- VAS pain and EQ-5D-3L **pain/discomfort**: the changes in scores are expected to have a strong positive correlation.

VAS global score

- VAS global score and EQ-5D-3L **index**: the changes in scores are expected to have a strong negative correlation.

VAS fatigue

- VAS fatigue and the EQ-5D-3L **index**: the changes in scores are expected to have a moderate negative correlation.
- VAS fatigue and EQ-5D-3L **mobility**: the changes in scores are expected to have a moderate positive correlation.
- VAS fatigue and EQ-5D-3L **self-care**: the changes in scores are expected to have a moderate positive correlation.
- VAS fatigue and EQ-5D-3L **daily activities**: the changes in scores are expected to have a moderate positive correlation.
- VAS fatigue and EQ-5D-3L **anxiety/depression**: the changes in scores are expected to have a moderate positive correlation.

DAS28/DAPSA/BASDAI/ASDAS

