- Disease activity measured with DAS28/DAPSA/BASDAI/ASDAS and the EQ-5D-3L **index**: the changes in scores are expected to have a moderate negative correlation.
- Disease activity measured with DAS28/DAPSA/BASDAI/ASDAS and EQ-5D-3L **mobility**: the changes in scores are expected to have a moderate positive correlation.

Karolinska Institutet – Research protocol: Follow-up with patient-reported outcome measures for improved health related quality of life – Construct validity and responsiveness of EQ-5D-3L in patients with rheumatic disease

- Disease activity measured with DAS28/DAPSA/BASDAI/ASDAS and EQ-5D-3L **self-care**: the changes in scores are expected to have a moderate positive correlation.
- Disease activity measured with DAS28/DAPSA/BASDAI/ASDAS and EQ-5D-3L **daily activities**: the changes in scores are expected to have a moderate positive correlation.
- Disease activity measured with DAS28/DAPSA/BASDAI/ASDAS and EQ-5D-3L **pain/discomfort**: the changes in scores are expected to have a moderate positive correlation.

HAQ-DI/BASFI

- Functional ability measured with HAQ-DI/BASFI and EQ-5D-3L **index**: the changes in scores are expected to have a moderate negative correlation.
- Functional ability measured with HAQ-DI/BASFI and EQ-5D-3L **mobility**: the changes in scores are expected to have a moderate positive correlation.
- Functional ability measured with HAQ-DI/BASFI and EQ-5D-3L **self-care**: the changes in scores are expected to have a moderate positive correlation.
- Functional ability measured with HAQ-DI/BASFI and EQ-5D-3L **daily activities**: the changes in scores are expected to have a moderate positive correlation.
- Functional ability measured with HAQ-DI/BASFI and EQ-5D-3L **pain/discomfort**: the changes in scores are expected to have a moderate positive correlation.

Karolinska Institutet – Research protocol: Follow-up with patient-reported outcome measures for improved health related quality of life – Construct validity and responsiveness of EQ-5D-3L in patients with rheumatic disease

Analysing EQ-5D-3L in patients who have improved versus patients who have not improved based on disease activity and functional ability

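### Should HAQ-DI/BASFI be held to a strong rather than a moderate correlation with EQ-5D-3L mobility, self-care and daily activities?

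*Combined protocol and SAP*

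**What the plan says.** Under Outcome measures, Functional ability, HAQ-DI and BASFI are said to "measure functional ability through questions about mobility, daily activities, and self-care".

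The section Convergent validity EQ-5D-3L has two levels. Related constructs need at least a moderate correlation (0.3 or more), while "constructs that are considered to be similar are expected to have a strong correlation" (0.5 or more). Each hypothesis line then carries one of the two labels. For function the line reads "Functional ability measured with HAQ-DI/BASFI and EQ-5D-3L mobility: a moderate positive correlation is expected"; self-care and daily activities are worded alike, and so is the pain line: "Functional ability measured with HAQ-DI/BASFI and EQ-5D-3L pain/discomfort: a moderate positive correlation is expected".

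The strong label appears elsewhere in the list: "VAS pain and EQ-5D-3L pain/discomfort: a strong positive correlation is expected". VAS global score with the index, and with EQ VAS, is also strong.

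The section Responsiveness EQ-5D-3L repeats the labels for change scores: "Functional ability measured with HAQ-DI/BASFI and EQ-5D-3L mobility: the changes in scores are expected to have a moderate positive correlation", against "VAS pain and EQ-5D-3L pain/discomfort: the changes in scores are expected to have a strong positive correlation".

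Study design and data collection sets the decision rule for each patient group: "75% of the hypotheses will need to be supported".

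**The concern.** On the plan's own description, the content of HAQ-DI and BASFI lies within three EQ-5D-3L dimensions. Those pairs look like the most natural candidates for the similar class, yet they get the lower bar. Function with pain/discomfort, which is outside the described content, gets the same bar. Pain with pain gets the higher one, for scores and for change scores, so the authors clearly use the distinction. No reason is stated.

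A correlation of 0.3 is 9% shared variance (0.3² = 0.09), against 25% at 0.5 (0.5² = 0.25). If the bar is too low, three pairs could count as support on weak evidence and help carry the instrument over the 75% line.

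**Working it through.** The plan gives no sample size or expected correlation to reproduce. The check has three parts: whether the labels break the plan's rule, how much of the count is affected, and when the bar would decide a verdict.

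**1. Labels against scope**

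| Pair | Scope of the two measures | Label |
|---|---|---|
| VAS pain, pain/discomfort | one pain question, one pain item | strong |
| VAS global, index | overall score, overall score | strong |
| VAS global, EQ VAS | overall score, overall score | strong |
| HAQ-DI/BASFI, mobility (likewise self-care, daily activities) | three-area score, one three-level item | moderate |
| HAQ-DI/BASFI, pain/discomfort | three-area score, item outside those areas | moderate |

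Strong is used only where the two measures match in scope. A score spanning three areas, set against an item on one of them, can reasonably be classed as related. With only two levels, it then shares a label with more distant pairs. The rule defines the related class by a floor, so a correlation above 0.5 also supports a moderate hypothesis.

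**2. Share of the count** (each slash-joined line counted once)

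- Convergent: VAS pain 5 + VAS global 1 + VAS fatigue 5 + disease activity 5 + function 5 = 21, of which 2 are strong and 19 moderate. Needed: 0.75 × 21 = 15.75, so 16. Share: 3/21 = 14.3%.
- Responsiveness: 21 + 2 AUC = 23. Needed: 17.25, so 18. Share: 3/23 = 13.0%.
- RA with convergent and known-groups validity pooled as construct validity: 21 + 5 (DAS28) + 5 (HAQ-DI) = 31. Needed: 23.25, so 24. Share: 3/31 = 9.7%.
- AS with BASDAI and ASDAS counted separately and BASFI as the function measure (assumption): convergent 21 + 5 = 26, needed 19.5, so 20; responsiveness 26 + 3 AUC = 29, needed 21.75, so 22.

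**3. When the bar decides the verdict**

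Let k be the number of other hypotheses supported, and m the number of the three correlations that are at least 0.3 but below 0.5, the rest being 0.5 or more. The verdict differs between the bars when k + 3 ≥ needed and k + 3 − m < needed.

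| Count | Needed | Others | k, m = 3 | k, m = 2 | k, m = 1 |
|---|---|---|---|---|---|
| Convergent, 21 | 16 | 18 | 13–15 | 13–14 | 13 |
| Responsiveness, 23 | 18 | 20 | 15–17 | 15–16 | 15 |
| RA pooled, 31 | 24 | 28 | 21–23 | 21–22 | 21 |
| AS convergent, 26 | 20 | 23 | 17–19 | 17–18 | 17 |
| AS responsiveness, 29 | 22 | 26 | 19–21 | 19–20 | 19 |

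Example: convergent, k = 15, m = 3 gives 18/21 = 85.7% under the plan's bar and 15/21 = 71.4% under 0.5.

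For any one pair, the chance of clearing a bar c is approximately 1 − Φ[(atanh c − atanh ρ)√(n − 3)]. Both n and the true correlation ρ are assumptions, and the formula is only approximate for a three-level item.

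| n | ρ | clears 0.3 | clears 0.5 |
|---|---|---|---|
| 100 | 0.40 | 0.870 | 0.108 |
| 500 | 0.35 | 0.894 | 0.000 |
| 500 | 0.40 | 0.995 | 0.003 |
| 500 | 0.45 | 1.000 | 0.075 |
| 500 | 0.55 | 1.000 | 0.938 |
| 2000 | 0.40 | 1.000 | 0.000 |

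In a large registry sample the choice of bar settles these three lines if the true correlations lie clearly between 0.3 and 0.5. It makes little difference if they lie well outside that band.

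**The case for a change.** The best case for a change is that the scope argument is the reader's and not the plan's. A difference in format did not stop the authors from expecting a strong correlation between one global question and an index built from five dimensions. Under the listed bars, a function scale need track mobility no better than a fatigue score does. Mobility, self-care and daily activities never face a strong hypothesis in either correlation analysis, although comparators described as covering them are available. Study design and data collection itself asks for expected magnitudes and clearly described constructs, and a sentence would cost nothing.

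Much of this stands. The rationale is absent, and for these dimensions the list is lenient. It does not follow that 0.5 is the right bar. The global question and the index differ in format, but both aim at overall health; a three-area score and a single-area item differ in what they cover. The description of HAQ-DI and BASFI is a one-sentence summary and names their construct as functional ability, not mobility as such. The reader can also see the classification, because the plan ties each class to a bar and every line states its bar.

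**Conclusion.** No stated rule is broken. The plan leaves the split between related and similar to the authors' judgement, makes that judgement line by line before analysis, and applies it alike to scores and change scores. Raising six lines (three for scores, three for change scores) to 0.5 would replace one defensible judgement with another on which reasonable statisticians differ. If results had already been seen, it would also weaken the standing of the a priori hypotheses; the documents do not say whether data have been extracted. A sentence giving the reason would help a reader but would alter no analysis or conclusion. If the correlations themselves are reported, anyone who prefers 0.5 can apply it.

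The three pairs make up 9.7% to 14.3% of a count, depending on how hypotheses are grouped. They decide a verdict only if one to three of the correlations fall between 0.3 and 0.5 and the remaining support lands in a window of one to three counts. This rests on counting slash-joined lines once, except in the AS variant shown, and on 75% being applied to each listed set or to the pooled RA set.
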